6. ANALYSIS

6.1. Proximate analysis

- A) Moisture content: An Al-cup will be dried at 104°cfor 30 minutes and cooled in a desiccator, and record the weight (W1). 3 g of the sample will then be added in the Al-cup and weighed (W2). The sample will then be dried for two hours at 139 °C. Then, the final dried sample will be weighed (W3) and recorded after cooling in a desiccator. The net moisture content of the sample will then be calculated using the following formula. %MC= ((W2-W1)-W3) ×100/ W1-W3 (%MC = percentage of net moisture content, W1= weight of Al-cup, W2= weight of sample before drying, W3= weight of sample after drying.
- **B)** Crude protein: The amount of protein present is calculated using the Kjeldahl method of protein analysis. The food sample will be weighed (0.5-1g) into a digestion flask. The sample will then be digested by heating it in the presence of sulfuric acid, a catalyst, copper (0.5g), and potassium sulfate (100g). Digestion will convert any nitrogen in the food into ammonia, and other organic matter to C0₂ and H₂0. After the digestion has been completed the

digestion flask will be connected to a receiving flask by a tube. The solution in the digestion flask will be made alkaline by adding sodium hydroxide, which converts the ammonium sulfate into ammonia gas. The ammonia gas that is formed will be liberated and mixed with boric acid. The low pH of the solution will convert the ammonia gas into the ammonium ion, and will simultaneously convert the boric acid to the borate ion. The nitrogen content will then be estimated by titration of the ammonium borate formed with standard hydrochloric acid using a suitable indicator to determine the end-point. The following equations will be used to determine the nitrogen concentration of a sample and corresponding crude protein percentage. $\%N = \{(Vs - Vb) * molecular weight of N * N Hcl\}/sample weight*10, % protein = 6.25* %N (Vs= sample volume, Vb= blank volume, N Hcl = normality of Hydrochloric acid.)$

- C) Ash content: A cruisable will first be weighed on electronic balance (W1). Afterward, 3g of food sample will be measured using an electronic balance (W2). The samples will then be put on the hot plate and charred and will be placed in a muffle furnace for 2 hours at 550°c. The final weight will then be measured after cooling it down (W3). The ash content will then be calculated using the formula: Ash $\% = W3 W1 \times 100 W2$
- D) Fat content (AOAC, 2000): Al-cup will first be heated for 30 minutes at 106°c, cooled on a desiccator, and weighed on electronic balance (W1). 1-5g of food sample will then be added on a thimble and weighed (W2). The thimble and Al-cup will be slot in the corresponding positions of the fat extraction unit. Subsequently, 70% of diethyl ether will be added to the sample in the thimble using a dispenser. The hot plate temperature will then be set at 500°cfor 20 minutes for soaking followed by the extraction step for 40 minutes. The third step will be the evaporation step. After the extraction step is complete, the extracted fat will be placed in an oven for 30 minutes at 106°c. The fat content will then be determined using the following formula (W3) % of fat= W3-W1 ×100 W2
- **E)** Total dietary fiber: duplicate portions will be incubated with pancreatic α- amylase and amyloglycosidase for 16 hr. at 370°c in a sealed 250ml bottle in shaking water. During this step, non-resistant starch will be solubilized and hydrolyzed to glucose and maltose by the combined action of the two enzymes. The reaction will then be terminated by PH adjustment and temporary heating. Protein in the sample will be digested with protease. For the measurement of high molecular weight dietary fiber, Ethanol or industrial methylated sprits

will be added and the insoluble and perceptible soluble dietary fiber will be captured, washed with ethanol and acetone, dried, and weighed. The final result will then be obtained by using the formula: Total dietary fiber (%) = (HMWDF+LMWSDF)/1000 (HMWDF = high molecular weight soluble dietary fiber LMWSDF= low molecular weight soluble dietary fiber)

6.2.Urine iodine analysis

Analytical methods consist of an initial digestion step to get rid of interfering substances, followed by the Sandell–Kolthoff reaction, of which the reading is obtained spectrophotometrically or colorimetrically. The digestion step will be held to remove Interfering substances in urine. The sample will be digested using the appropriate strong acid (e.g. ammonium persulphate). The oxidizing step will be carried out in a heated environment. The Sandell–Kolthoff reaction is a two-step reaction in which the rate of reaction will be measured during the reduction of the yellow-coloured ceric ions by arsenic in the presence of iodide to form colourless cerous ions and elemental iodine.

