2.2. Specific objectives

The specific objectives of this study are to:-

- 1. Evaluate the nutrient profile of diets using proximate analysis.
- 2. Determine the nutritional status (i.e. stunting, wasting, underweight and overweight)of children diagnosed using anthropometric measurements.
- 3. Assess the dietary diversity score (DDS) of children using food frequencyquestioners (FFQ).
- 4. Examine the urine samples of children to identify the urine iodine (UI) level.
- 5. Assess the parents and caregivers perceptions about the Eating behaviour of ASD children using questioner.
- 6. Evaluate the ASD severity level and developmental growth of children with ASD in correlation to UI level.

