6.3. Statistical analysis plan

Given the variability of the type of data generated from each assessment, data analysis and interpretation shall be done in the respective the nature of each data.

Anthropometric measurement data shall be analyzed using corresponding index of Weight for height, height for age, weight for age and MUAC for age and interpreted using international standards. ENA 2020 shall be used to record the measurements and convert to respective Z-scores.

The Data generated from CARS diagnosis will be on a scale from one (normal behavior) to four (severely abnormal behavior) for each category of questions. The scores between 30 and 37 indicate mild to moderate ASD, while scores between 38 and 60 indicate severe ASD. These results shall be analyzed by SPSS version 26 for descriptive statistics and correlations

In case of urine iodine analysis, the decrease in yellow color over a fixed period is measured by a colorimeter with an appropriate filter or with a spectrophotometer and plotted against a standard

curve constructed with known amounts of iodine. The resulting reading of iodine content shall then be compared among case and control groups of the study. SPSS version 26 shall be used to for descriptive statistics, significant difference and correlations

The data generated from proximate analysis of food samples shall be recorded for each analysis and calculated for average. The final figure represents the amount of nutrient present per 100 gm. thus amounts consumed by children. This data shall then be compared among case and control groups of the study. SPSS version 26 will also be used for descriptive statistics, significant difference and correlations

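### The moisture formula divides by cup weight minus dried weight instead of the wet sample weight, so the result depends on the cup used

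*Combined protocol and SAP*

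**What the plan says.** Section 6.1, item A, sets out three weighings. The empty dried Al-cup is W1. For the next weight the text reads "3 g of the sample will then be added in the Al-cup and weighed (W2", which makes W2 cup plus wet sample. After drying, "the final dried sample will be weighed (W3) and recorded after cooling in a desiccator".

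The formula for percentage moisture content is "MC= ((W2-W1)-W3) ×100/ W1-W3", with this legend: "W1= weight of Al-cup, W2= weight of sample before drying, W3= weight of sample after drying".

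The result serves the first specific objective in section 2.2: "Evaluate the nutrient profile of diets using proximate analysis". On the proximate results, section 6.3 says "The final figure represents the amount of nutrient present per 100 gm", and then "This data shall then be compared among case and control groups of the study".

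**The concern.** Moisture content is water lost divided by wet sample weight. The printed numerator can be read as water lost. The printed denominator is made from the cup and the dried material, and the wet sample weight does not appear in it. The weight of a piece of laboratory equipment therefore enters a figure that is meant to describe food.

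The legend adds a second difficulty. It describes W2 as the sample before drying, while the procedure weighs the sample in the cup and the formula subtracts the cup from W2. The text also does not say whether W3 is taken in the cup.

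If the formula is applied as written, the moisture result is not an amount per 100 g of food. It varies with the cup, and the case-control comparison of moisture is distorted.

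**Working it through.** The documents contain no worked moisture value, so there is no figure to reproduce. The check evaluates the printed formula against the standard definition.

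**Inputs**
- Sample weight: 3 g (section 6.1, item A).
- Cup weight W1: not given; assumed 5, 10, 30 and 50 g, with 20 g added in step 4.
- True moisture m: not given; assumed 10% to 85%.
- Comparator: water lost × 100 / wet sample weight.

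**1. Most favourable reading: W2 = cup + wet sample, W3 = dried sample without the cup, denominator in brackets**

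Numerator: (W2 − W1) − W3 = 3 − 3(1 − m) = 3m, which is exactly the water lost.

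Denominator: W1 − W3 = W1 − 3(1 − m). It should be 3.

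At 70% moisture, W3 = 0.9 g and water lost = 2.1 g. At 60%, W3 = 1.2 g and water lost = 1.8 g.

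| Cup (g) | Printed result, true 70% | Printed result, true 60% | True 10-point gap becomes |
|---|---|---|---|
| 5 | 2.1/4.1 = 51.2% | 1.8/3.8 = 47.4% | 3.9 |
| 10 | 2.1/9.1 = 23.1% | 1.8/8.8 = 20.5% | 2.6 |
| 30 | 2.1/29.1 = 7.2% | 1.8/28.8 = 6.3% | 1.0 |
| 50 | 2.1/49.1 = 4.3% | 1.8/48.8 = 3.7% | 0.6 |

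Gaps are computed from unrounded values.

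**2. When the printed formula is right**

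It requires W1 − 3(1 − m) = 3, so W1 = 3(2 − m):
- 5.7 g at 10% moisture
- 4.5 g at 50%
- 3.9 g at 70%
- 3.45 g at 85%

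**3. Whether one standard cup would help**

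With a 3.9 g cup throughout:
- true 10%: 0.3/1.2 = 25.0%
- true 50%: 1.5/2.4 = 62.5%
- true 70%: 2.1/3.0 = 70.0%
- true 85%: 2.55/3.45 = 73.9%

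The cup that is right for one food is wrong for the others.

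**4. Other readings of the weights, true moisture 70%**

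| W2 | W3 | Printed formula becomes | 5 g cup | 20 g cup |
|---|---|---|---|---|
| with cup | with cup | (2.1 − W1)/(−0.9) | 322.2% | 1988.9% |
| without | without | (2.1 − W1)/(W1 − 0.9) | −70.7% | −93.7% |
| without | with cup | (2.1 − 2·W1)/(−0.9) | 877.8% | 4211.1% |

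Taking the operators literally (divide by W1, then subtract W3) does not remove the cup either. On the weights of step 1 a 5 g cup gives 210/5 − 0.9 = 41.1. That reading also subtracts grams from a percentage.

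Nor is this a dry-basis formula: the dry-basis value at 70% moisture is 2.1/0.9 = 233.3%, whatever the cup.

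**5. Corrected denominator**

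On the reading of step 1, ((W2 − W1) − W3) × 100/(W2 − W1) = 3m × 100/3 = 100m. At 70% this is 2.1/3 = 70.0%, for any cup.

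**The case against.** The strongest reply is that this is probably a slip of transcription with little practical effect. The numerator is correct on the natural reading, and the prose describes ordinary drying and weighing. Results such as 4% for a moist food, or values below zero or above 100%, might well be noticed before any comparison was made. That is plausible, but section 6.1 makes the printed formula the method of calculation, so the written rule should be right.

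A second reply is that the formula may have been damaged when the text was extracted. The neighbouring ash and fat formulas have visibly lost symbols. Here the brackets, slash and minus signs are present, and a lost symbol would not turn W2 − W1 into W1 − W3. Damage cannot be excluded entirely, but it is an unlikely explanation.

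Two limits do stand. First, the shrinkage of group differences belongs to the reading in step 1. If W3 is weighed with the cup, a 5 g cup gives (1.8 − 5)/(−1.2) = 266.7% at 60% moisture against 322.2% at 70%, so the 10-point gap widens to 55.6 points. What holds in general is dependence on the cup, not the direction of the distortion. Second, the reach is narrow: protein, ash, fat and fibre have their own formulas, none of which uses moisture, and the anthropometric, dietary diversity, urinary iodine and CARS results are unaffected.

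**Conclusion.** The concern holds. No reading of W2 and W3 makes the printed denominator the wet sample weight except by coincidence, and no reading gives a result free of the cup. That conclusion is algebraic and needs no assumed values.

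The size depends on cup weights and food moisture that the documents do not state. Over the assumed cups of 5 to 50 g, on the most favourable reading, the printed formula understates a true 70% by about 19 points (70 − 51.2 = 18.8) to 66 points (70 − 4.3 = 65.7).

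The error is confined to the moisture figure and its comparison between groups. It should be corrected before moisture results are calculated or reported. It does not threaten the rest of the study.

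**What to change.** Keep W2 as cup plus wet sample, as the procedure has it, and use the form that matches how W3 is weighed:

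- W3 = dried sample without the cup: %MC = ((W2 − W1) − W3) × 100 / (W2 − W1).
- W3 = cup plus dried sample: %MC = (W2 − W3) × 100 / (W2 − W1).

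State which applies, print the denominator in brackets, and reword the legend so that W2 and W3 each say whether the cup is included.

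The cost is one formula line and its legend. W1, W2 and W3 are already part of the procedure, so no extra laboratory work is needed. Any moisture results already calculated can be recomputed from the recorded weights, provided these were kept and it is known whether W3 included the cup.

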6.3. Statistical analysis plan

Given the variability of the type of data generated from each assessment, data analysis and interpretation shall be done in the respective the nature of each data.

Anthropometric measurement data shall be analyzed using corresponding index of Weight for height, height for age, weight for age and MUAC for age and interpreted using international standards. ENA 2020 shall be used to record the measurements and convert to respective Z-scores.

The Data generated from CARS diagnosis will be on a scale from one (normal behavior) to four (severely abnormal behavior) for each category of questions. The scores between 30 and 37 indicate mild to moderate ASD, while scores between 38 and 60 indicate severe ASD. These results shall be analyzed by SPSS version 26 for descriptive statistics and correlations

In case of urine iodine analysis, the decrease in yellow color over a fixed period is measured by a colorimeter with an appropriate filter or with a spectrophotometer and plotted against a standard

curve constructed with known amounts of iodine. The resulting reading of iodine content shall then be compared among case and control groups of the study. SPSS version 26 shall be used to for descriptive statistics, significant difference and correlations

The data generated from proximate analysis of food samples shall be recorded for each analysis and calculated for average. The final figure represents the amount of nutrient present per 100 gm. thus amounts consumed by children. This data shall then be compared among case and control groups of the study. SPSS version 26 will also be used for descriptive statistics, significant difference and correlations

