4. SUBJECTS

Selection of 26 children with Autistic Spectrum Disorder (ASD) (case group) and the corresponding 26 typically developing children (control group), 52 children in total, shall be made on the basis of:

4.1.Inclusion criteria

- a) Children that are already diagnosed with ASD for the "case" group,
- b) Children fulfilling the matching criteria to the case group (i.e. age and sex) for the control group.

4.2.Exclusion criteria

- a) Use of special supplements,
- b) Use of heavy medication,
- c) Children with critical chronic disease such as cancer, HIV AIDs.

4.3.Test conditions

The subjects shall:

- a) Be of school age;
- b) Legal guardians of the child need to Sign a consent form for the willingness of his/her participation;
- c) Give the necessary information and specimen agreed upon in the given consent forms.

The analysis shall:

a) Be conducted by

- The researcher as per guidelines and procedures described for all nutritional analysis.
- Registered nurse for urine sample collection
- Registered physician for CARS diagnosis.
- b) Have no risk involved since it doesn't involve any penetration to the human muscle
- c) Be done with the willingness of the participant and their legal guardians (he/she can stop the participation anytime)

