5. PROCEDURE

5.1. Height

A child height board will be used to measure height of the children. The children will be measured with minimal clothing and no shoes and socks must be worn. The feet must be together, arms to the side, legs straight and shoulders relaxed, the head must be in the Frankfort horizontal plane (looking straight ahead). An average of 3 readings will be taken and read to the nearest 0.1 cm.

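### Wasting and overweight in school-age children rest on weight-for-height, an index that ignores age; BMI-for-age is not in the plan.

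*Combined protocol and SAP*

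**What the plan says.** Objective 2 (section 2.2) reads "Determine the nutritional status (i.e. stunting, wasting, underweight and overweight)of children diagnosed using anthropometric measurements". Section 4 sets the sample: "Selection of 26 children with Autistic Spectrum Disorder (ASD) (case group) and the corresponding 26 typically developing children (control group), 52 children in total". Under section 4.3 each child must "Be of school age", and no range in years is given anywhere. In the inclusion criteria age appears only as a matching variable: "Children fulfilling the matching criteria to the case group (i.e. age and sex) for the control group".

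Section 6.3 names four indices: "Anthropometric measurement data shall be analyzed using corresponding index of Weight for height, height for age, weight for age and MUAC for age". They are to be "interpreted using international standards", and "ENA 2020 shall be used to record the measurements and convert to respective Z-scores". The section does not name the reference or its valid range. It gives no z-score cut-off, does not say which index defines which condition, and has no rule for a child outside the reference. BMI-for-age is not mentioned.

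Height and weight are both measured (sections 5.1 and 5.3).

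**The concern.** An index for overweight, or for low weight relative to body size, has to separate a heavy child from a tall one. Of the four listed indices only weight-for-height does this, and it does so without using age. In school-age children the expected weight at a given height shifts with age and maturation. The same score can therefore mean different things in two children several years apart. A stunted older child is compared with younger children of normal height, and stunting is itself one of the outcomes.

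Half of the conditions in a named objective are at stake. Followed as written, section 6.3 would classify wasting and overweight on an age-blind scale. If the reference has an upper limit, it would also leave gaps or extrapolated values with no stated way of handling them.

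**Working it through.** **Plan's own figure.** The only relevant number is the sample size: 26 + 26 = 52, which agrees with section 4. The documents give no prevalence, cut-off, age range or reference limit, so nothing numerical about the indices can be reproduced.

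**Step 1: which index can carry which condition.** Section 6.3 gives no mapping, so this is inferred from what each index measures.

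| Listed index | Inputs | Condition it can carry |
|---|---|---|
| Height-for-age | height, age, sex | stunting |
| Weight-for-age | weight, age, sex | underweight; cannot tell tall from heavy |
| MUAC-for-age | arm circumference, age, sex | possibly thinness; no cut-off or school-age reference stated |
| Weight-for-height | weight, height, sex | wasting, overweight |

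Overweight has no other candidate in the list. Wasting has one partial alternative, MUAC-for-age.

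**Step 2: age-blindness.** Weight-for-height is a function z = f(weight, height, sex). Two children of the same sex, weight and height get the same z whatever their ages. BMI-for-age is z = g(weight/height², age, sex). The same two children have the same BMI, but each is compared with children of the same age. This step needs no assumption about where a reference stops.

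**Step 3: what an upper limit would do.** Assume that the reference or the software conversion stops at age L, and that ages are spread evenly from a to b. Neither L nor the age range is in the documents. Then

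share out of range = (b − max(a, L)) / (b − a), held between 0 and 1.

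Worked examples for ages 6–12: with L = 7, (12 − 7)/6 = 83%, about 43 of 52; with L = 10, (12 − 10)/6 = 33%, about 17 of 52.

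| Assumed ages (years) | L = 5 | L = 7 | L = 10 | L = 11.5 |
|---|---|---|---|---|
| 4–8 | 75% (39) | 25% (13) | 0% (0) | 0% (0) |
| 5–10 | 100% (52) | 60% (31) | 0% (0) | 0% (0) |
| 6–12 | 100% (52) | 83% (43) | 33% (17) | 8% (4) |
| 7–14 | 100% (52) | 100% (52) | 57% (30) | 36% (19) |
| 5–18 | 100% (52) | 85% (44) | 62% (32) | 50% (26) |

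Counts out of 52 are in brackets. The result runs from none of the children to all of them.

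**Step 4: who would be missing.** Under an age limit, loss depends on age, and cases and controls are matched on age. Under a height limit, loss depends on stature, which is not matched and is related to an outcome. If the software extrapolates, no value is missing but the values lack support from the reference. The documents do not say which of these applies.

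**The case against.** The strongest reply is that the reference is unspecified rather than wrong. Section 6.3 only says that the indices are "interpreted using international standards", and the link from wasting and overweight to weight-for-height is inferred. MUAC-for-age could serve for low nutritional status. Matching on age and sex would make any age-driven loss similar in the two groups. Section 6.3 spells out a case-control comparison for iodine and food data but not for anthropometry; such a comparison follows only from the general objective. No primary endpoint is declared, and nothing is irretrievably lost, because BMI can be derived later from the recorded weight and height.

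Much of this stands, and it limits both the size and the severity of the point. It does not remove it. Whatever reference is chosen, weight-for-height takes no account of age, and the listed set offers no other index for overweight.

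A reader might go further and infer that objective 2 as a whole cannot be answered, that most of the children would have no valid z-score, or that those who do would be selectively the youngest and shortest. The documents support none of these. Stunting and underweight do not use weight-for-height. A majority affected depends on ages and limits that are not stated. Selection on stature would arise only under a height limit.

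**Conclusion.** The point holds for two of the four conditions in objective 2: clearly for overweight, and for wasting to the extent that MUAC-for-age does not replace weight-for-height. The plan commits to an age-blind index in school-age children when an age-specific one is available from the same measurements. This rests on the stated index list and on the premise that expected weight at a given height changes with age and maturation in this age group.

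Missing or extrapolated z-scores are a conditional addition, to be settled by checking the reference and the software against the ages enrolled. No single percentage should be quoted for it.

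This should be fixed before analysis, so that the index and cut-offs are not chosen after the data are seen. It is not critical to the study, because the data needed for the better index are already recorded.

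**What to change.** In section 6.3:

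- State the enrolled age range in years, and name an international reference and software that cover it.
- Replace weight-for-height with BMI-for-age z-scores for thinness and overweight, computed from weight, height and age.
- Take height-for-age from the same reference. Use weight-for-age only within its reference ages.
- Report MUAC as a raw value adjusted for age and sex, unless the chosen MUAC reference covers these ages.
- Assign one index and one cut-off to each condition, and say how a child outside a reference will be handled.

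In objective 2, reword wasting as thinness (low BMI-for-age).

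Before dropping or keeping ENA 2020, enter a few children across the enrolled ages and heights and see what it returns.

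The cost is a change of wording and possibly of conversion software. No new measurement is needed: weight and height are already taken, and age must be known for matching and for the age-based indices already planned. The downside is that results will be less directly comparable with weight-for-height figures from surveys of younger children.

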5.4. Urine collection

60 ml. urine samples will be collected from each child by a trained clinical practitioner (nurses), at the child's period of urinary stimulation, using sample collection cups.

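### Controls are matched to cases on age and sex, but Section 6.3 does not carry the matching into the urine iodine and nutrient comparisons, so some precision may be lost

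*Combined protocol and SAP*

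**What the plan says.** Section 4 plans 26 children with ASD and "the corresponding 26 typically developing children (control group), 52 children in total". The control criterion in 4.1 is "Children fulfilling the matching criteria to the case group (i.e. age and sex) for the control group". It does not say whether matching is by individual pair or by frequency, and it gives no age tolerance. Section 4.3 limits all children to school age, without limits in years.

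In Section 6.3 the urine iodine analysis is: "The resulting reading of iodine content shall then be compared among case and control groups of the study". The analysis of food composition is: "This data shall then be compared among case and control groups of the study". On method, the food paragraph says "SPSS version 26 will also be used for descriptive statistics, significant difference and correlations", and the iodine paragraph has an almost identical sentence. No test, paired method, regression or covariate is named for either outcome. Age appears in 6.3 only through the anthropometric indices ("Weight for height, height for age, weight for age and MUAC for age"), and sex does not appear there at all.

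**The concern.** Matching makes the two groups alike in age and sex, so the part of the outcome that age and sex explain largely cancels from the difference between group means. A plain two-group test does not know this. It estimates its standard error from the full within-group spread, including the age and sex part, and so overstates the uncertainty. The design effort of matching then yields balance but not the precision that comes with it.

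The stake is efficiency. With 26 children per group there is little power to spare, and age and sex must already be recorded in order to match.

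**Working it through.** **The plan's own figure.** 26 + 26 = 52 is correct. No alpha, power, effect size or SD is stated, so there is no power calculation to reproduce.

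**Inputs.** From Section 4: 26 per group, matched on age and sex. Assumed: two-sided 5%; normal outcomes with equal variance; a true difference of 0.6 within-group SD; R², the share of within-group variance explained by age and sex, from 0 to 30%.

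**Adjusted comparison (regression on group, age, sex).** Residual df = 52 − 4 = 48, and SE = √(2(1 − R²)/26) in SD units. Power comes from the noncentral t with noncentrality 0.6/SE. At R² = 10%: SE = √(1.8/26) = 0.263, noncentrality = 0.6/0.263 = 2.28, critical t = 2.011, power = 60.8%. Interval width relative to unadjusted is √0.90 × 2.011/2.009 = 0.95.

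**Unadjusted comparison under close matching.** The difference has true variance 2(1 − R²)/26, but the test uses the pooled variance s², which averages 1. Pair sums carry variance in proportion to 1 + R² and pair differences in proportion to 1 − R². So s² is distributed as [(1 + R²)χ²₂₅ + (1 − R²)χ²₂₅]/50, with the two chi-squares independent. Power and type I error were obtained from 400,000 draws, with critical t on 50 df.

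| R² | Power, unadjusted | Power, adjusted | Gain (points) | CI width ratio | Type I error, unadjusted | Detectable at 80% power, unadjusted → adjusted (SD) |
|---|---|---|---|---|---|---|
| 0 | 56% | 56% | −0.1 | 1.00 | 5.0% | 0.79 → 0.79 |
| 5% | 57% | 59% | 2 | 0.98 | 4.4% | 0.79 → 0.77 |
| 10% | 57% | 61% | 4 | 0.95 | 3.9% | 0.78 → 0.75 |
| 20% | 57% | 66% | 9 | 0.90 | 3.0% | 0.77 → 0.71 |
| 30% | 58% | 72% | 14 | 0.84 | 2.0% | 0.755 → 0.66 |

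Gains come from unrounded powers: 58.5 − 56.6 = 1.9; 60.8 − 56.8 = 4.0; 65.9 − 57.0 = 8.9; 71.7 − 57.7 = 14.0. At R² = 0 the only change is 50 to 48 df (56.43% to 56.36%). Adjustment breaks even at R² of about 0.2%, computed at a 0.8 SD difference.

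**Sensitivity, by simulation (ages 6–14 and 75% boys assumed).**
- *Type of matching.* At R² = 10% and 30%, adjusted power is 61% and 72% both with matching within one year and with frequency matching in two-year bands by sex.
- *Wrong age form.* With a U-shaped age effect fitted as linear, adjusted power is 58% and 64% (R² = 10%, 30%), against 56% and 58% unadjusted. Adjusted type I error is 4.5% and 3.7%.
- *Four controls missing (assumed), R² = 10%.* Regression 57%, unadjusted 53%, paired test on the remaining 22 pairs 52%.
- *Pairs also share something unmeasured (assumed 20% of variance), R² = 5%.* The paired test has 25 df and noncentrality 0.6/√(2 × 0.75/26) = 2.50, giving 67%. The regression gives about 60% and the unadjusted test 57%.
- *Pairs share only age and sex, R² = 10%.* Paired 59%, regression 61%.

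**The case against.** The strongest reply is that the defect is conditional. Section 6.3 names no test, so a paired or adjusted analysis is unstated rather than ruled out. That stands: a reader might infer that the plan commits to an unpaired t-test, and the text does not support this. What remains is that the plan matches on two variables and then describes the comparison without them.

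Second, the gain may be negligible. R² and the 0.6 SD difference are both assumptions. All the children are of school age, and the nutrient value is content per 100 g of food, which a child's age and sex may hardly predict. This also stands, and it is why the rows for R² of 0 and 5% matter as much as those for 20% and 30%. One argument should not be added: Section 5.4 does not say how many urine samples each child gives, so a small R² cannot be argued from a single sample.

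Third, a reader might infer that ignoring the matching biases the result or inflates false positives. It does neither in a comparison of means: matching that succeeds balances age and sex, and the type I error falls below 5%.

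Fourth, a reader might infer that the regression recovers all the precision from matching and so makes pairing redundant. The U-shaped and shared-factor checks contradict this. Which analysis does better depends on what the pairs share, and the documents do not settle that.

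**Conclusion.** The point holds as a low-cost improvement in efficiency, not as an error of validity. If the two comparisons are run as plain two-group tests, they are unbiased with respect to age and sex but conservative, with intervals about 2% wider than needed at R² = 5%, 5% at 10% and 19% at 30% (1/0.976, 1/0.950 and 1/0.838). The size depends wholly on R², which the documents do not give, and the power figures also depend on the assumed 0.6 SD difference and on roughly normal outcomes. The recommendation rests on the asymmetry: a cost of about 0.1 point of power if age and sex are irrelevant, against a gain of 2 to 14 points over R² from 5% to 30%.

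**What to change.** In Section 4, state whether controls are matched as individual 1:1 pairs or by frequency, and the age tolerance.

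In Section 6.3, make the case–control comparison of urine iodine, and of each nutrient's average per child, a linear regression on group with age and sex as covariates. Report the adjusted difference with its 95% CI. Fix the scale for urine iodine in advance (for example log), and define how the food samples are averaged to one value per child. This sets the form of each comparison; it does not make every nutrient a primary outcome.

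If matching is by individual pair, record a pair identifier and let the main analysis respect it: a paired test, or a mixed model with a pair term plus age and sex, which keeps children whose match is missing. Pairing should not then be only a sensitivity analysis.

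Cost: SAP wording and, for 1:1 matching, one extra data field. The regression spends two degrees of freedom and assumes a form for the age effect. A wrong form reduces the gain, although in the U-shaped check the regression still did no worse than the unadjusted test.
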